6.2.2. Accessible population

Patients with thermal burns admitted to the burn unit of the Río Hortega Hospital in Valladolid since March 2020 who do not meet exclusion criteria. Sand reached 30 patients admitted in 2018 for thermal burns. Although the unit, a reference in Castile and León for the care of burn patients, serves a population of 2,419.00 inhabitants

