6.2.3. Sampling design

Sampling in the selection of patients shall be per snowball, all participants in the centre shall be included until sample saturation or until 18 months after the start of the study, in which metabolic expenditure will be assessed in all 3 cases: passive external overheating, thermal plate overheating and convective air blanket overheating.

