6.2.4. Sample size

Using the GRANMO sample matingc, Version 7.12 was calculated for the difference of media coupled in energy expenditure at rest of the combination of passive and active external (in two methods, by thermal plate and convective air blanket) versus passive external heating.

Accepting an alpha risk of 0.05 and a beta risk of 0.2 in a bilateral contrast, 34 subjects are required to detect a difference equal to or greater than 0.15 units. A standard deviation of 0.3 is assumed. A 5% tracking loss rate has been estimated.

The difference expected to be found in the resting metabolic expenditure rate of at least 0.1 times the GMB. The increase in baseline metabolic expenditure of these patients in studies with burned patients was 1.4 times with standard deviation of 0.2 - 0.32 times. The sample will be adjusted to the standard deviation values presented in the pilot sample.

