6.2.5. Inclusion criteria

- Patients over the age of 18.
- Patients with thermal burns.
- Patient with high burn criteria according to ABA:
 - o 2nd grade burn
 - Patient 18 59 years: SCQ > 20 %
 - Patient > 60 years or pathology: SCQ > 10 %
 - o 3rd degree burn
 - SCQ > 10 %
- Patients in mechanical ventilation.

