6.4.3 Pilot test

A pilot test will be carried out with at least 2 patients to check the proper collection of variables and debugging of errors in the collection methods and the adequacy of the heating application times and inclusion of the variables.

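### Section 6.2.4 lets the pilot SD change the sample size with no direction or floor, while the only pilot described guarantees just two patients

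*Combined protocol and SAP*

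**What the plan says.** Section 6.2.4 sizes the study for a paired comparison of resting energy expenditure: "Accepting an alpha risk of 0.05 and a beta risk of 0.2 in a bilateral contrast", a difference of 0.15, an assumed SD of 0.3 and 5% loss, giving 34 subjects. It reports that the rise in metabolic expenditure in earlier studies of burned patients "was 1.4 times with standard deviation of 0.2 - 0.32 times". It ends with "The sample will be adjusted to the standard deviation values presented in the pilot sample". No direction, minimum, maximum, formula or timing accompanies that sentence.

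Section 6.4.3 is the only place that describes a pilot: "A pilot test will be carried out with at least 2 patients to check the proper collection of variables and debugging of errors". It also mentions heating application times and the variables to include. Estimating an SD is not among its purposes. The two sections do not refer to each other, so treating the pilot sample in one as the pilot test in the other is an inference.

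Section 6.2.3 sets the end of recruitment: "all participants in the centre shall be included until sample saturation or until 18 months after the start of the study". It gives no minimum number.

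**The concern.** The closing sentence of 6.2.4 is a commitment, and its natural reading is that the paired-means calculation will be repeated with the pilot SD in place of 0.3. Nothing in the plan prevents a chance low SD from taking the sample below 34. An SD from two patients has one degree of freedom and says almost nothing about the true value. Its distribution is also skewed, so a small pilot underestimates the SD more often than it overestimates it. A team that followed the sentence in good faith could stop well short of the number that the plan itself says is needed.

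**Working it through.** **Inputs.** From 6.2.4: difference 0.15, SD 0.3 (it must be the SD of paired differences for 34 to follow), two-sided alpha 0.05, power 0.80, loss 5%. From 6.4.3: a pilot of at least 2. Assumptions: normally distributed differences, a true SD of 0.3, and revision both up and down.

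**Step 1: the plan's own figure.** n = (1.960 + 0.842)² × (0.3/0.15)² = 7.849 × 4 = 31.4, rounded up to 32 evaluable. Allowing for loss, 32/0.95 = 33.7, so 34. The stated number reproduces. By the paired t distribution, 32 evaluable patients give 78% power, so 78% is the fair comparator for the t-based figures below.

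**Step 2: the rule as a formula.** With a pilot SD of s, N = 7.849 × (s/0.15)² / 0.95, rounded up.

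**Step 3: how variable s is.** For m pilot patients, s² is distributed as 0.3² × χ²(m−1)/(m−1). With m = 2, the 95% confidence interval for the true SD runs from 0.45 to 31.9 times the observed SD. The recalculated N has a median of 16, and its middle half runs from 5 to 45.

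**Step 4: consequence for N and power.** One million simulated pilots for each m; power from the two-sided paired t test with 0.95N evaluable (at least 3, so that power is defined) and no cap on N:

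| Pilot patients | N below 34 | Mean power |
|---|---|---|
| 2 | 68% | 49% |
| 5 | 59% | 66% |
| 10 | 56% | 72% |
| 20 | 54% | 75% |
| N kept at 34 | n/a | 78% |

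Capping N at 45 lowers the two-patient figure to 47%. The cap is 30 × 1.5 years, reading 6.2.2 ("Sand reached 30 patients admitted in 2018 for thermal burns") as 30 thermal-burn admissions in a year, before eligibility and consent.

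**Step 5: a milder case, for illustration only.** If s were held between 0.2 and 0.32, N would run from 15 (14.69 rounded up) to 38 (37.60 rounded up). It would be 15 in half of two-patient pilots, with about 41% power there, and mean power would be 58%. The plan sets no such limit. The 0.2 to 0.32 range also reads as a spread between patients, not the SD of within-patient differences, so these figures should not carry the argument.

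**Step 6: a larger SD.** With 32 evaluable patients and an SD of 0.4, the difference detectable at 80% power is about 0.20.

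**The case against.** **The pilot may be larger.** The plan's two patients are a minimum. That is right, and the loss against 78% shrinks to about 6 points with 10 patients and 3 points with 20. It does not vanish, and the documents promise no more than two.

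**The sponsor may intend upward revision only, or would never accept an absurd number.** Either is possible. A reader might infer that the trial will run at under 50% power. The documents do not support that: the figure depends on a mechanical two-way rerun and on including samples that no team would use. What stands is that the text permits a reduction and sets no limit to it.

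**Recruitment may decide the sample anyway.** The 30 yearly admissions are counted before the large-burn criteria and before "Patients in mechanical ventilation" is applied, and no eligible fraction is given. If only 15 could be enrolled, a recalculated N of 15 and a rule to enrol everyone would give the same power, about 42%. The floor matters only if accrual would otherwise pass the reduced number. Sample saturation in 6.2.3 is undefined, so equating it with the recalculated N is also an inference.

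**The effect size is unsettled.** Section 6.2.4 also expects a difference of at least 0.1. At an SD of 0.3 that needs 7.849 × (0.3/0.1)² = 70.6, so 71 evaluable and 75 with loss. A floor of 34 is therefore sound only at 0.15. This stands and is carried into the fix.

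**Conclusion.** The point holds as a defect in the adjustment rule. It is not an error in the 34, which follows from the stated inputs. A two-way adjustment from the only pilot described would put N below 34 in about 68% of two-patient pilots. Mean power would be about 47 to 49% in that worst case and 66 to 75% with 5 to 20 pilot patients, against about 78% with N kept at 34. These results rest on a true SD of paired differences of 0.3, a difference of 0.15, normality, revision in both directions, and the two sections meaning the same pilot.

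A reader might also infer that a floor raises power to 81 or 82%. It does not: that figure requires N to be revised upward as well, to as many as 45. With N simply kept at 34, power is about 78% by paired t, or 80% by the normal approximation.

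**What to change.** Replace the last sentence of 6.2.4 with: *The pilot SD will not be used to reduce the sample below the calculated size (34 at a difference of 0.15 and an SD of 0.3).* The number should follow whichever difference, 0.15 or 0.1, is retained when that section is reconciled. Use the 6.4.3 pilot only for its stated purpose. If a later SD estimate is larger and N cannot rise within the 18 months, restate the detectable difference, as in Step 6.

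The change costs one sentence and no patients beyond the planned 34. The sponsor gives up the option of a smaller trial: if the SD of paired differences were really 0.2, the same formula needs 15, so the floor would keep 34 − 15 = 19 more patients than necessary. It does not solve recruitment, and it has no effect if accrual stays at or below the reduced number.

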6.2.5. Inclusion criteria

- Patients over the age of 18.
- Patients with thermal burns.
- Patient with high burn criteria according to ABA:
 - o 2nd grade burn
 - Patient 18 59 years: SCQ > 20 %
 - Patient > 60 years or pathology: SCQ > 10 %
 - o 3rd degree burn
 - SCQ > 10 %
- Patients in mechanical ventilation.

6.2.6 Exclusion criteria

- Sepsis criteria according to ABA.
- Application of debridenenzymatic (data in the next 24 hours).
- 6 hours after surgery.
- After 2 hours after healing the burns

Patients in hemorrhagic shock.

6.3. Variables

Sociodemographic data will be collected from the patients included in the study: age, sex, days of entry into burn unit, early and hospital mortality. Personal background data, previouspathologies. Variables about the burn will be included: Body Surface (BSA) in m², Burned Body Surface (SCQ) in m² and %, Deep Burned Body Surface (SCQP) in %, origin of the burn.

6.3.1. Dependent variables

At the stage of defining thermal comfort, the variables shall be collected:

- Operating temperature (Dry temperature + radiant temperature)
- Relative humidity
- Air speed

For the assessment of nutritional data and energy expenditure, the variables will be collected: Weight, Height, Ideal Weight, BMI (kg/m²), FiO₂, Charlson Index, Nutri- Score, Nutritional Biochemistry, Serum Albumin (g/dl). The calculation of theoretical caloric requirements (kcal/day) using the Penn State predictive formula and the protein requirements/day (gr/day) calculation will be included.

- Metabolic expenditure, calculated by Indirect calorimetry collecting the variables:
 - VCO₂: Carbon dioxide production (Avg VCO₂, VCO₂ hp)
 - VO₂: Consumption of O₂ (Avg VO₂, VO₂ HP)
 - o RQ: Cociente respiratorio (Avg RQ, Avg EE)
 - EE: Energy expenditure in kcal/d (Avg EE/m², AVG EE/Kg)
- Body temperature via surface thermometer
- Central temperature recorded by bladder probethermometer, from entry and registration c/8h until 7 days after admission. Time recording of temperature during heating analysis.
- Calculation of liquid loss estimation.

The difference of the metabolic state at rest versus the actual one will be categorized by qualitative scale.

Due to the critical condition of the patient, the CONFORT scale will be collected for the evaluation of sedation and pain in the critical patient.

For the assessment of the comfort status (NOC 2008) and thermoregulation (NOC 0800) according to Thert scale will be carried out in the application of the two heating techniques.

6.3.2. Independent variables

- Passive external heating: Ambient temperature value in oC Programmable ambient temperature, with ambient temperature programming capability in range of 18 to 35 oC with accuracy of +-0.1oC, and driven pressure of +15 Pa..
- Active external heating:
 - By radiant plate: Patient distance, heating level and control temperature on skin.
 Application time.
 - Aspira Medical AB Aragonia thermal plate ® MTC 400 CE 0413 certified. It is a height heating device adjustable up to 50 cm from the patient generates radiant heat at low temperature (up to 39oC) evenly distributed. It is equipped with an adjustable potentiometer of 0- 9 and has a temperature probe on the skin as a control and safety mechanism.
- Convective air blanket: Application start, Heating power level (35-38-43oC). Application time
 - Equator Level 1® of Smiths Medical REF EQ-5000, CE 0473 certified, consisting of a unit that produces hot air and adjustable forced air from 38oC to 43oC.. It sends the hot forced air distributed by tubular blanket that convectively heats the patient by spreading the hot air directed towards the patient through the textile pore of the air blanket.
- Factors that decrease hyper-metabolic response:
 - Blood glucose monitoring.
 - Administration of Glutamine Supplement⁵⁹.
 - o B-blocker drugs: propanolol, oxandrolone... (Dismimuirán the GMB)
 - o Caloric dose of enteral nutrition. (Sufficient, scarce augmented by the

6.4. Instruments collecting information

Climate comfort measurement

Testo® 435 multifunction air conditioning meter, which performs the necessary measurements to adjust the ventilation and air conditioning systems⁷⁵. The different pluggable sensors and probes will provide the variables to study::

- Thermal speed probe: air speed and volumetric flow rate.
- IAQ (Indoor Air Quality) probe to evaluate air quality measures CO2, ambient temperature, ambient humidity and absolute pressure.
- Balloon probe to measure thermal radiation
- Temperature probe to measure ambient temperature, indoor temperature and surface temperature. Both with measurement accuracy +/- 0.1 oC
- Location of measures
 - At patient bed level:
 - 4 measurement points and extrapolate the results assuming radiant symmetry conditions, would allow to extrapolate results to the entire object area: patient's head and trunk and staff positions at the patient's head and trunk height
 - 2 radiant plate positions: the nearest (50 cm) and 1 meter, distance when the worker's position is simulated in the patient's environment.
 - At the worker's level: 2 positions, at the bedside and on the patient's trunk 50 cm from the center of the bed.
 - Media of the convective air blanket in the functions of 380 and 43oC, calculating temperature, humidity and speed..

Calculation of metabolic expenditure by Indirect Calorimetry and Temperature:

- o Carescape R860® of Datex Ohmeda CE certified with the GE Healthcare Adult D-Lite+ Spirometry Kit with CE 0537 certification. GE CARESCAPE™, is a fan that has an integrated module that can measure the energy expenditure of patients through indirect calorimetry⁷⁶.
- Central temperature:
 - Vesical probe with 16fr MDCON SV temperature sensor registered in Philips Monitor®
 IntelliVue MP5.
- Body temperature:

0

6.4.1 Data collection sheet

The study variables will be collected in the Microsoft Excel database® as seen in *Annex 1.*. Patients shall be coded with an assigned number that does not permit identification by a specific independent sheet intended for this purpose.

A collection sheet model for data collection will be distributed with explanatory instructions for research partners.

For the collection of sociodemographic data and study variables, it will be necessary to access the patient's medical history with the data that are entered into the program and those automatically recorded to the Philips Intelli Vue® medical history.

6.4.2 Data collection

For the analysis of thermal comfort, the suppliedam biennage temperatureshall be analysed in the values: minimum of 25oC, 28oC, 31oC as shown in Table 6... The ambient temperature of 33oC is obvious, as it is considered that in combination with the elements of active external overheating average conditions of 33oC are reached. The graphical representation of the

Table 6: Scenario of combination analysis of heating methods

	Ambient temperature		
Registration No.	25oC	28oC	31oC
Thermal plate at 50 cm	1	3	5
Thermal plate at 100 cm	2	4	6
Convective air blanket 38oC			
Convective air blanket 43oC			

measures shall be carried out as represented in *Annexess IV* and *V*.

The convective air blanket, by the heating mechanism, an analysis will be carried out, studying the theoretical effect combined with the ambient temperature.

Sociodemographic and nutritional data of the patient will be collected after acceptance and signature of the informed consent that will be collected in the first days after the patient's entry into the burn unit. Variables will be collected during the night shift (22:00 to 8:00) because there are no scheduled tasks of cures, diagnostic tests or surgical intervention that may alter both the care activity in the unit and the alteration of variables to be collected. Data will be collected for 6 hours from the intervention: evolution of body and central temperature and metabolic expenditure calculated in 24 hours. From the third day after the burn, the 3 heating methods will be applied to study, on three consecutive nights

Study Protocol, Statistical Analysis Plan (SAP), Informed Consent Form (ICF). Version 1.0

Night 1: Ambient temperature 32oC

Night 2: Ambient temperature and combination with thermal plate

Night 3: Ambient temperature and combination with thermal blanket.

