Clinical Optimization of Ambient Temperature and Heating Methods in Caring in Major Burns Patients

Optimal Heating Temperature in Major Burns Patients

MSN [name]

Universitat Rovira i Virgili
Sanidad Castilla y León
Hospital Universitario Rio Hortega Valladolid
Universidad de Valladolid
[contact]

Study Protocol, Statistical Analysis Plan (SAP), Informed Consent Form (ICF)

Version 1.0

Marchy, 2020

HeatingBurns01- Study Protocol, Statistical Analysis Plan (SAP), Informed Consent Form (ICF)

1. Material and methods

6.1 Design, methodology and justification:

Pre-experimental pre-experimental epidemiological study without control group, in large burnt patients that will evaluate the influence on the metabolic expenditure of the inclusion of active external overheating in the control of ambient temperature adjusted to thermal comfort.. Two methods of active external heating, thermal plate and convective air blanket shall be used. Metabolic expenditure shall be measured by indirect calorimetry in the usual treatment with passive external overheating and post-intervention in the combination of passive and active external warming.

Sand pre-study the combination of passive and active external overheating by measuring the operating temperature in various cases for optimal application, as well as the definition of thermal comfort in the unit of large burns. In this way, two study stages are integrated as shown in *Table 5.*.

Table 5: Study stages Clinical optimization of ambient temperature and heating methods in the care of the patient large burned according to thermal comfort

Stage 1	Stage 2
Empirical study of operating temperature according to the	Quasi-experimental study of large burned patients to study
combination of passive and active external heating methods for the definition of environmental comfort.	the impact on metabolic expenditure of the inclusion of active external overheating in environmental temperature
methods for the definition of environmental connoct.	control

6.2. Population and sample:

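### Recording opens when the device is switched on, so Nights 2 and 3 have no same-night calorimetry under passive heating, and 6.5 does not adjust for the state in which the patient enters each night

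*Combined protocol and SAP*

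**What the plan says.** Section 6.1 (Design, methodology and justification) sets the contrast: "Metabolic expenditure shall be measured by indirect calorimetry in the usual treatment with passive external overheating and post-intervention", the latter being passive combined with active heating.

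Section 6.4.2 gives the schedule. From the third day after the burn, "the 3 heating methods will be applied to study, on three consecutive nights". The list opens with "Night 1: Ambient temperature 32oC", followed by the plate on Night 2 and the blanket on Night 3. Collection takes place in the night shift, 22:00 to 08:00. For the window itself the text is "Data will be collected for 6 hours from the intervention", covering "evolution of body and central temperature and metabolic expenditure calculated in 24 hours". I read the last phrase as a rate per 24 h, since 6.3.1 gives energy expenditure in kcal/d; the wording could also mean a 24 h measurement and should be clarified.

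For core temperature, 6.3.1 specifies recording "from entry and registration c/8h until 7 days after admission. Time recording of temperature during heating analysis".

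Section 6.4 describes the ventilator as having an "integrated module that can measure the energy expenditure of patients through indirect calorimetry", and 6.2.5 requires mechanical ventilation for inclusion.

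Section 6.5 compares means by Student t or Mann-Whitney U. It names no baseline value and no covariate.

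**The concern.** The effect of a device is the difference between a heated reading and what the same patient would have shown under passive heating at that time. As written, the passive reading comes from one or two nights earlier. Whatever has changed in the patient between those nights enters the device contrast.

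Some of that change is random and only widens the difference. Some may be systematic, because every patient follows the same listed order during the days after a major burn. Section 6.3.2 itself lists influences on the hypermetabolic response that may vary between nights, such as beta-blockers, glutamine and the caloric dose of enteral nutrition. A passive reading taken just before switch-on would show how much the starting point had moved. A reading not taken on the night cannot be reconstructed later.

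**Working it through.** **Inputs.** From 6.2.4: two-sided alpha 0.05, beta 0.2, difference 0.15, SD 0.3, 5% loss, 34 subjects. From 6.4.2: a 6 h record, a 10 h shift, three consecutive nights. Assumed, because the documents give no value: the mean shift in entry state between nights; the correlation ρ between the between-night difference in the pre-heating reading and that in the heated reading; and an SD of 0.3 for both differences.

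**1. The plan's sample size.** n = (0.3 × 2.8016 / 0.15)² = 31.4, so 32; 32 / 0.95 = 33.7, so 34. This reproduces the stated figure, with 0.3 read as the SD of the paired difference. With 32 evaluable patients the standard error is 0.3/√32 = 0.0530. The paired t test (31 df, noncentrality 0.15/0.0530 = 2.83) has 78% power.

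**2. Timing.** The Night 1 reference precedes the plate by about 24 h and the blanket by about 48 h. The shift leaves 10 − 6 = 4 h outside the record.

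**3. What a shift in entry state does to the unadjusted contrast.** With no device effect, noncentrality = shift / 0.0530, 31 df:

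| Assumed mean shift | Share of 0.15 | Probability of p < 0.05 |
|---|---|---|
| 0.025 | 17% | 7% |
| 0.05 | 33% | 15% |
| 0.10 | 67% | 45% |

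**4. What covariate adjustment does to power.** The residual SD is 0.3√(1−ρ²). The adjusted device effect is the intercept at zero baseline difference, with variance σ²(1/n + x̄²/Sxx) on 30 df, where x is the baseline difference. The average variance inflation is 1 + (n·m²/0.3² + 1)/(n − 3), with m the mean baseline difference. For m = 0 this is 1 + 1/29 = 1.034. For m = 0.10 it is 1 + (3.556 + 1)/29 = 1.157. Power for 0.15, averaged over the sampling of the baseline, against 78% unadjusted:

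| ρ | Residual SD | Power, m = 0 | Power, m = 0.10 |
|---|---|---|---|
| 0.1 | 0.298 | 77% | 73% |
| 0.3 | 0.286 | 81% | 76% |
| 0.5 | 0.260 | 87% | 84% |
| 0.7 | 0.214 | 96% | 94% |

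**5. Raw change scores instead.** The SD of the difference in within-night changes is 0.3√(2(1−r)), with r the same correlation. At r = 0.3 it is 0.355 and power falls to 64%. At r = 0.5 it is 0.300 and power is again 78%. Change scores should not carry the inference.

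**6. How much bias the adjustment removes.** With equal SDs the slope equals ρ, so a mean baseline shift m is corrected by ρ·m. At ρ = 0.5 and m = 0.10, 0.05 is removed. If the whole shift carries into the heated reading, 0.05 remains.

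**The case against.** The strongest reply is that this is an ordinary within-patient design. Night 1 supplies a planned passive value for every patient. Random night-to-night variation belongs to the SD of paired differences, and 34 reproduces on that reading, so the noise is already budgeted. The plan also limits the nuisance: it chooses nights without scheduled procedures (6.4.2), excludes sepsis and recent surgery, wound care or enzymatic debridement (6.2.6), and records a sedation and pain scale (6.3.1) and enteral caloric dose (6.3.2). Nothing in the text forbids a pre-heating reading. All of this stands, and it is why the point is an improvement and not the repair of an invalid design. It does not answer a systematic shift between nights, which the SD does not cover and 6.5 does not model.

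Three stronger readings are tempting and are not supported:

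- A reader might infer that the trial has no pre-heating value at all. It has one: Night 1 is passive heating only.
- A reader might infer from the 8-hourly schedule that the last core temperature before heating can be 8 h old. That is only the worst case of the routine schedule. Section 6.3.1 adds timed recording during the heating analysis, the series in 6.4.2 can include a value at time zero, the bladder probe registers on the monitor (6.4), and 6.4.1 gives access to automatically recorded data. The gap concerns calorimetry.
- A reader might infer that a same-night baseline always improves precision. Step 4 shows that it does not when ρ is low or mean entry state differs between nights.

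The baseline also has limits as a remedy. It does not remove carry-over or all effects of the listed order. If the plate's effect persisted into Night 3, adjusting for that night's pre-heating value would bring it into the blanket contrast.

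**Conclusion.** The concern holds for metabolic expenditure on Nights 2 and 3. No same-night passive calorimetry is scheduled, the reference is one or two nights old, and the analysis has no term for entry state. An undetected mean shift of 0.05 to 0.10 would raise the false-positive rate from 5% to about 15% to 45%. Whether a shift of that size occurs cannot be judged from the documents.

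The value of a baseline depends on ρ. With no mean shift, the gain over 78% power is nil at about 0.1, roughly 3 points at 0.3, 9 at 0.5 and 18 at 0.7. With a mean shift, precision may fall slightly and the adjustment serves mainly to reduce bias, in part only. These figures rest on 32 evaluable patients, 0.3 as the SD of the paired difference, equal SDs for the baseline and heated differences, and assumed values of ρ and of the shift. The sample size of 34 is unaffected. This is a cheap improvement worth making before recruitment.

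**What to change.** **In 6.4.2:** add about 1 h of calorimetry and bladder-temperature recording immediately before switch-on on Nights 2 and 3, and at the same clock hour on Night 1, then record the planned 6 h. Take the reading under whatever passive heating the patient is already receiving; record the ambient temperature during that hour and do not set a new one for the purpose. State that expenditure is expressed in the same unit before and during heating, and clarify the 24 h wording.

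**In 6.5:** analyse each device-versus-passive paired difference with the difference in the same nights' pre-heating values as a covariate, the device effect being the intercept at zero baseline difference. Show within-night changes for all three nights descriptively only, with Night 1 as the no-device course.

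**Cost:** one more hour of recording per night (7 h of a 10 h shift) on equipment the patient is already connected to, a pre-heating value per outcome and night on the data sheet, and a sentence or two of analysis. To end by 08:00 the 6 h record must open by 02:00, so the pre-heating hour must start by 01:00, and it must also respect the post-surgery and wound-care windows in 6.2.6. Precision falls slightly if the baseline proves weakly correlated. Carry-over and the single listed order need separate attention.
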